- Secondary outcomes: HIV treatment linkage (yes/no) and ART initiation (yes/no) for those testing HIV positive, each variable individually in the primary composite outcome (i.e. counseling, PrEP), sexual behavior (consistent condom use, number of partners).
- Exploratory Outcomes: include alcohol/substance use, PEP use, STI testing/treatment, and type of prevention or treatment care site accessed (i.e. HST vs. other).

Finally, the following outcomes will be reported by study arm: HIV knowledge, HIV- and MSM-stigma, risk-perception, self-efficacy, social support, intention to obtain HIV test in next one month, and SMT engagement by arm (proportion of all messages viewed, website visit, and any communication with online-peer counselors).

11. Plans to identify contamination across study arms. Contamination will be assessed by using a content recall questionnaire^{86,87} to measure any diffusion and sharing of **CHALO! 2.0** and attention matched control contents, determining whether participants report sharing messages or website links. Participants will also be asked if they knew anyone participating in the study and if they received any contents from them.⁹⁵ Members from the HST and Einstein research teams will assist in building research instruments.

12. Randomization checks and missing data. A member from either the Einstein or HST team will first review and summarize data using descriptive summaries and graphical analyses to ensure that reported values are within appropriate ranges, check for outliers and abnormal values, and verify that distributions of measures meet

assumptions of planned statistical tests. The Einstein and HST research teams will also explore whether **CHALO! 2.0** and the 2 control groups are equivalent on potential confounders (e.g., sexual identity, income, age, education, intention to test, and sexual behaviors. If these variables differ between groups, we will include them as covariates in multivariable analyses (see Section C.7.4). For missing categorical data, we will use multivariate multiple imputation using the fully conditional specification method.⁹⁶ We will repeat imputations 5 times, and then compare statistical results using datasets that include imputed values and the dataset that drops missing values. This will guide interpretation of our assessment of the impact of missing data on our study findings, as well as our interpretation of overall results.

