1.1 CHALO! 2.0 (intervention arm): MSM randomized to this arm will receive 2x-weekly digital media messages for 12 weeks (24 messages total) about HIV, HIV-testing, and HIV prevention and treatment. Messages will target information, motivation, and behavioral skills, as we did for the **CHALO!** pilot. Digital media will combine text messages, infographics, and brief videos (<30 seconds), with each message containing a link to the study specific webpage listing testing resources and MSM specific services offered by HST. Messages will convey information (HIV knowledge, logistical information about testing/care, PrEP), enhance motivation (i.e., brief video clip creating a social norm for HIV testing), and build behavioral skills (i.e., brief video clips demonstrating how to how to request and obtain a HIV test at HST or the private lab using the digital coupons), and provide interaction with online peer counselors (who will be reachable by the same WhatsApp channel/number that participants receive intervention contents). The study team will guide finalization of exact messaging contents, based on input from HST's two community advisory boards. Researchers at HST will use WhatsApp Business App⁵⁷ to deliver prescheduled messages and collect process data.

1.2 Attention matched control (AMC): MSM randomized to this arm will receive informational messages also sent out 2x-weekly using the WhatsApp Business App. Message formats and delivery will be matched to the **CHALO! 2.0** arm (i.e., same number of video clips, infographics, text messages, sent in the same pattern), but contents will differ from **CHALO! 2.0** and will focus on the top health priorities identified by participants in our 2017 online survey: diabetes, hypertension, obesity, nutrition, and stress management.

1.3 Digital coupon only control: MSM randomized to this arm will receive, at study entry, the digital coupon and a resource webpage link, and then will receive follow-up study assessment surveys. They will be eligible for prize drawings based on completion of assessments.

Table 1. Overview of study arms and components.

Components	CHALO! 2.0	Attention matched control	Digital coupon only
Contents of digital-media sent 2x/week for 12 weeks	HIV, testing, prevention, treatment, linkage-to-care	general health information	--
Personalized digital coupon for free testing	✓	✓	✓
Webpage listing testing/care sites, contact information for online peer-counselors	✓	✓	✓

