6. **Recruitment.** The researcher staff at HST will use similar procedures for recruitment as we have used in prior studies: online ads will be displayed on MSM dating apps in Mumbai (Grindr, Blued, others if a new popular app emerges) and by targeted ads on Instagram to men in Mumbai with LGBTQ/gay interests associated with their profiles. All ads will contain links directing potential participants to a webpage with further information about the study and an eligibility screener. Eligible participants will be directly linked to an informed consent page (including an audio-video version of the informed consent) on Avegen's Health Machine (HM), a web-based survey platform,⁶³ and non-eligible participants will be directed to an exit page thanking them for their interest. Eligible participants who agree to participate after reading the informed consent will be directed to a baseline survey. All potential participants will provide a phone number associated with their WhatsApp account and an email address, and reply to a confirmation code (sent immediately to confirm the individual is real and not a bot or a computer program). Phone numbers will be checked against HST's registry by research staff to ensure participants aren't already receiving services through HST. Eligible participants will receive their incentive and be considered fully enrolled within 48 business hours.

6.1 Feasibility of recruitment: In prior studies of MSM in Mumbai, HST enlisted community members to help design ads to recruit MSM at high risk of HIV. For the **CHALO!** Pilot, HST enrolled 244 MSM in Mumbai over 3 weeks, and for Zero Meters Away online survey, we enrolled 1036 sexually active MSM from Mumbai in over 4 weeks (46% of whom would have met inclusion criteria for the proposed study and provided mobile numbers). Recruitment for this trial will be enhanced because all participants will receive an incentive (unlike our 2017 online study) and because of the continual increase in SMT use by Indian MSM. We plan to enroll approximately 100 participants per month (which will be controlled by the frequency of online recruitment ads); this rate will ensure that study staff can verify participants and that HST's testing sites and counselors are not overwhelmed by potentially large influxes of individuals needing services in a short time.

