6.2 Unique Participants and non-fraudulent data: Fully online studies risk enrolling fraudulent participants,⁶⁴⁻⁶⁸ and] precautions will be taken to avoid such participants. First, the only way individuals will learn about the study and start the screener will be by clicking on a direct link from an MSM networking app or social media site with ads only displayed in Mumbai. Based on our prior experiences in India and the US, the likelihood is exceptionally low of fake accounts “trolling” MSM dating apps or having a Facebook or Instagram profile with attached LGBTQ interests, then being invited into a research study and successfully “guessing” the enrollment criteria. Second, our screening survey will be able to block multiple submissions from the same device.⁶⁹ Third, eligibility screener will contain attention questions and include items beyond the inclusion criteria (e.g., smoking, substance use, other health issues) to prevent individuals from “guessing” eligibility criteria. Fourth, participants will verify their mobile number and email address (found to be acceptable to Indian MSM).^{23,24,43} Fifth, baseline and follow-up surveys will also include attention questions. Finally, study staff will manually review all flagged surveys for suspicious responses, check for duplicate emails and mobile numbers, compare responses from the same IP addresses, and examine those from proxy-IP addresses.⁷⁰ These protocols are based on what we and others have used (NIH K23MH102118, NIH UG3AI133675).^{23,67,71}

6.3 Tracking and retention: The research team at HST will collect information at baseline about whether and how peer-counselors should identify themselves when calling or texting (e.g., by name, “the research study,” or the

“CHALO! project”), particularly for participants who test HIV-positive. Participants will receive automatic reminders for completing the pre-specified follow-up surveys at 3, 6, 12, and 18 months.

6.4 Regular incentives: Participants will receive increasing incentives for each complete assessment at months 3, 6, 12 and 18; the research team at HST will ensure acceptability of incentives by offering choices (PayTM – e-cash widely used in India and connected to mobile number,⁷² or Amazon.co.in gift-code) (see Table 1 for amounts).

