6.7 Snowball Recruitment: If a participant requests a screening/enrolment link to share with their network at any time, we will share a customized link to the Chalo!2.0 study information page. They can request this link either by texting/WhatsApp on the study phone number or by contacting our VPeers on a recruitment platform. If a participant does not request a link by the 3-month mark of enrolment in the study, we will proactively ask participants whether they are willing to share a customized link among their network, via WhatsApp or SMS. All links lead to the Chalo! 2.0 study information page. Rationale: Participants may already be sharing screening/enrolment links among their network. This strategy allows us to monitor when participants refer other individuals to the study. We will not provide any monetary benefits/ support for sharing the link.

7. Randomization and blinding. Subjects meeting all eligibility criteria will be randomized to one of three study arms. Participants will be assigned either to **CHALO! 2.0** (intervention), to an Attention-Matched Control, or to a Digital Coupon for free HIV testing only arm. After baseline survey completion, The research team at HST will use random blocked design, with a fixed block size, to stratify randomization by prior HIV testing history (never tested vs. not tested in >6 months). To further minimize bias in group allocation and analysis, a data manager who has no contact with study participants will (1) assign them to study group (intervention or controls), (2) notify our technology consultant of group assignment by providing the consultant each week with a list of mobile numbers and which set of contents each number should be programmed to receive, and (3) store allocation sequences in a password-protected encrypted file. Participants will be unaware of arm assignment and will receive automated messages to complete online surveys. Study staff collecting HIV testing and linkage-to-care outcomes will also be blinded to study arm. Finally, HST’s online peer counselors and navigators will not be informed of study hypothesis.

8. Data Collection.

Table 2: Data sources and measures						
Measure	Study Instrument	Assessment Month				
Outcomes: HIV testing and linkage to care		0	3	6	12	18
HIV testing	Lab report (via digital coupon); self-report	●	●	●	●	●
Linkage to prevention/treatment (PrEP, counseling, ART)	HST’s healthcare worker log; HST clinic record; self-report	●	●	●	●	●
Covariates						

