>99%	0.15-0.4	0.05-0.1	0.03-0.01
>98%	0.3-0.4	0.1-0.2	0.03-0.01
>90%	0.3	0.15	0.1-0.15
>70%	0.2	0.1	0.08
>49%	0.3	0.2	0.2
>21%	0.15	0.1	0.1

*power is for CHALO! compared to each control separately

months, explore

whether participant factors and testing strategy predict HIV prevention (counseling or PrEP use) and treatment (ART initiation). For secondary and exploratory outcomes (defined in C7.1), we will repeat analyses as above, using ANOVA for or chi-square tests as appropriate.

13.4 Aim 2 sample size considerations: We anticipate that there will be no higher than 7% prevalence of undiagnosed HIV. Combined with expected HIV testing rates by 12 months of at least 75%, 45%, and 35% in the three arms, we anticipate the available sample size of HIV-uninfected participants for Aim 2 to be **CHALO! 2.0** ($n_1=247$), attention-matched control ($n_2=139$), and digital coupon ($n_2=108$). Based on HST's current linkage-to-care rates for HIV- negative individuals (30%),⁹⁰ we expect the rate of linkage-to-prevention care at 12 months to be 30% for **CHALO!** vs. 15% for attention-matched control vs. 5% for digital coupon only. The study's 2 main effects (**CHALO!** vs. Attention-matched control and **CHALO! 2.0** vs. digital coupon only) have >90% and >99% power, respectively (Table 4). We also provide power estimates for smaller effect sizes. The power was calculated using PASS software V15.0., with a two-tailed alpha of .025, resulting in a family-wise error rate of at most 0.05 for the primary outcome in the Aim 2. Due to an expected overall small number of individuals testing HIV- positive, we will not have power to detect potential differences between arms.

PROTECTION OF HUMAN SUBJECTS

A. RISKS TO HUMAN SUBJECTS

A1. HUMAN SUBJECTS INVOLVEMENT, CHARACTERISTICS, AND DESIGN.

A1a. Proposed human subject involvement. The protocol will include a 3-arm parallel, single blind, pragmatic randomized control trial of an online HIV digital messaging intervention (CHALO! 2.0) compared to an Attention-Matched Control, or a Digital Coupon only. Through online surveys, HIV testing utilization and results, and clinic visit data tracked by HST healthcare workers during the 12-week intervention period, and during the 15 months of follow-up, we will evaluate the outcomes for CHALO! 2.0.

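### Section 7 fixes one block size per stratum, and nothing withholds it from HST staff who review applicants; undisclosed, varying block sizes would remove most certain prediction at almost no cost

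*Combined protocol and SAP*

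**What the plan says.** **Allocation.** Section 7 (Randomization and blinding) describes three arms and two strata: "The research team at HST will use random blocked design, with a fixed block size, to stratify randomization by prior HIV testing history". No size is stated. Section A1e describes the randomisation again and says nothing about the block size or who knows it.

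**Safeguards.** Under Section 7 a data manager with no participant contact makes the assignments, keeps the sequence in an encrypted file and gives a technology consultant a weekly list of numbers and their content sets. Participants and the staff collecting outcomes are blinded. Online peer counselors are kept from the hypothesis only. Section A1a calls the study a "3-arm parallel, single blind, pragmatic randomized control trial".

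**Where arm could show.** Section 1.1 has HST researchers use the WhatsApp Business App "to deliver prescheduled messages and collect process data". The content is HIV-related in one arm and general health in another, and the coupon-only arm gets none. Section 1.1 also provides online peer counselors, "who will be reachable by the same WhatsApp channel/number that participants receive intervention contents". Under Section 2.1 each participant, once verified, receives a link to a webpage specific to his arm.

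**Where staff affect admission.** Section 6 has phone numbers compared with HST's "registry by research staff to ensure participants" are not already its clients. Section 6.2 adds that "study staff will manually review all flagged surveys for suspicious responses, check for duplicate emails and mobile numbers", and that shared and proxy IP addresses are examined.

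**The concern.** Encrypting the list hides future assignments only as long as they cannot be worked out from past ones. With one block size throughout, anyone who knows that size and the earlier assignments in a stratum can tell when the remaining places in a block all belong to one arm. An applicant's stratum is known, because it comes from his reported testing history.

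What matters is whether such a person could also influence admission. Reviewing a flagged survey or a shared IP address takes judgement. A reviewer who knew the next arm could treat a borderline applicant differently according to how likely he seemed to get tested. The primary analysis in Section 13.1 is a chi-square comparison of the proportions tested by 6 months, so selection of that kind would enter it directly. Section 12 plans adjustment for measured baseline differences, which cannot be relied on to remove selection on an unrecorded impression.

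**Working it through.** The plan gives no predictability figure, so there is none to reproduce.

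**Inputs from the documents.** Three arms and two strata (Section 7); equal allocation, implied by 300 per arm at 6 months (Section 13.2); 1,000 participants (Participants); about 100 enrolments a month (Section 6.1); weekly release of assignments (Section 7).

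**Assumptions.** Block size B = 3m, with B from 3 to 12. The guesser knows B and the order of assignment within the stratum. A stratum holds 25%, 50% or 75% of enrolments.

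**Step 1. Worst case: every earlier assignment visible at once.** An assignment is certain when all places left in the block belong to one arm. The chance that the last k places all belong to one arm is

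P(k) = 3 × C(3m − k, 2m) / C(3m, 2m).

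Summing P(k) over k = 1 to m gives 3m/(2m + 1) certain places per block. Dividing by 3m gives a certain share of 1/(2m + 1).

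| B | Certain share | Best-guess success (chance = 33%) |
|---|---|---|
| 3 | 1/3 = 33.3% | 61% |
| 6 | 1/5 = 20.0% | 56% |
| 9 | 1/7 = 14.3% | 53% |
| 12 | 1/9 = 11.1% | 51% |

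Best-guess success comes from exact recursion over the places left. For B = 3 it is (1/3 + 1/2 + 1)/3 = 61%. Larger blocks give less certainty: 9.1% at B = 15 and 7.7% at B = 18.

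**Step 2. Assignments visible only through the weekly list.** Enrolment is 100 × 12/52 = 23.1 a week. At the start of a week the expected number of certain places in a stratum is about Σ k·P(k)/B. Dividing by the stratum's weekly enrolment gives the certain share.

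- B = 3: 1/3 = 0.333. In a half-size stratum, 0.333/11.54 = 2.9%.
- B = 12: (1 + 0.545 + 0.164 + 0.024)/12 = 0.144, and 0.144/11.54 = 1.3%.

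Simulation with Poisson weekly arrivals agrees:

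| Stratum's share of enrolments | B = 3 | B = 6 | B = 9 | B = 12 |
|---|---|---|---|---|
| 25% | 5.7% | 4.1% | 3.0% | 2.5% |
| 50% | 2.9% | 2.1% | 1.6% | 1.3% |
| 75% | 1.9% | 1.3% | 1.0% | 0.8% |

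Best-guess success in this setting is 35% to 43%. The certain share varies inversely with enrolment rate, so halving enrolment would roughly double it.

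**Step 3. Randomly varying sizes, full history visible.** Simulating 500 per stratum, with the guesser knowing the set of possible sizes:

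| Sizes | Certain share | Best-guess success |
|---|---|---|
| 3/6 | about 9% | not computed |
| 3/6/9 | 3.9% | 56% |
| 6/9/12 | 2.5% | 53% |

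Comparing like with like (full visibility), certainty falls from 11–33% to 2.5–4% for the two wider sets. The best guess hardly moves: 6/9/12 at 53% matches a fixed block of 9.

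**The case against.** The strongest reply is that the documents keep the relevant roles apart, or at least do not join them. The data manager has no participant contact, and a technology consultant receives the weekly list. The messages are prescheduled. Nothing identifies the HST researchers who deliver them with the staff who check the registry or review surveys. Peer counselors have no documented admission role, and Section B3a bars them from raw survey responses. Eligibility comes mainly from an online self-report screener, and registry and duplicate checks are largely factual look-ups. Section 7 randomises only people who meet all criteria, and recent use of HST services is an exclusion (Section A1c), so the registry check should already precede assignment. Varying the sizes also does not make guessing hard: under full visibility a 3/6/9 mix (56%) is easier to guess than a fixed block of 12 (51%).

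Most of this stands. A reader might infer that HST staff both see earlier assignments and decide who is admitted, or that up to a third of assignments are in fact predictable. The documents support neither: the first is an inference from message delivery and arm-specific links, and the second needs small blocks and full, immediate visibility. The reply does not fill the gap, however. No section withholds the block size, separates survey and IP reviewers from those handling arm-specific content, or says that fraud review ends before assignment. Arm-specific links sent after contact verification could also show an arm sooner than the weekly list does.

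**Conclusion.** The point holds as an avoidable weakness in allocation concealment. The fixed block size is explicit, and the documents leave open who knows it and who can see past assignments.

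The size depends on what staff can see. With blocks of 12 down to 3, it is 11–33% certain under full visibility with a known block size, and about 1–6% if the weekly list is the only route and enrolment runs at about 23 a week. Partial visibility would fall between the two. All these figures rest on assumed block sizes.

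A reader might go further and conclude that the primary comparison is biased. That is not supported: no passage shows anyone with both the knowledge and the discretion, and the number of applicants whose admission turns on judgement is not given. The reason to act is that the remedy costs almost nothing.

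**What to change.** - In Section 7, replace the fixed block size with permuted blocks of randomly varying size within each stratum, in multiples of 3 and including larger sizes (6/9/12, for example). State that the sizes are not disclosed to HST staff who screen applicants or have participant contact, and record them only in the data manager's restricted file.
- State that registry, duplicate and flagged-survey checks on an applicant are complete before the data manager opens the next assignment.
- If enrolment is under way, apply both changes to the remaining blocks.

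The cost is a few sentences and a regenerated list, with no added participants. Balance loosens slightly. An unfinished block of 12 can put one arm at most 4 ahead of another in a stratum, so at most 2 × 4 = 8 over both strata, against about 1,000/3 = 333 per arm. The change removes most certain knowledge of the next arm but does little to the success rate of an informed guess.

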While Einstein is the coordinating site for the study, all research related activities will take place at the international site, The Humsafar Trust (HST), in Mumbai, India. The activities conducted at HST include recruitment, informed consent, enrollment and follow-up, as well as intervention delivery. The HST site will be responsible for all data collection. The Einstein team provided assistance building study protocol and will provide consultation for the development of study materials including survey questionnaires. Both research staff from Einstein and HST will participate in data analysis. Einstein staff, including the PI ([name]) will not have access to any identifying information.

Participants: Researchers at HST will recruit 1000 individuals who meet the following eligibility criteria: (1) ≥ 18 years old; (2) live or work in the Mumbai metropolitan area, including Thane; (3) fluent in Hindi or English, (4) identify as cis male, (5) anal sex with men in past 1 year; (6) (a) report that they have either never tested for HIV, (b) are unaware of HIV test results, or (c) are HIV-negative with last HIV test ≥ 6 months ago at any time and anal sex since last test; (7) able to provide and verify a WhatsApp mobile number and email address; (8) willing to answer online surveys for 18 months; and (9) have not participated in a prior HIV research study (by self-report).

Procedures

1. Description of 3 trial arms.

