Retention will be enhanced by (1)utilizing Whatsapp for intervention and online survey delivery since all incoming mobile phone calls text messages are free in India, which will allow participants to receive all study communications and will remove the burden for participants to appear go to a study site to complete the surveys (2) collecting information in the baseline assessment about whether and how peer-counselors should identify themselves when calling or texting (e.g., by name, "the research study," or the "CHALO! project"), particularly for participants who test HIV-positive, (3) providing incentives completing online surveys (at 0,3,6,12, 18 months) in increasing amounts (\$6.20, \$7.75, \$8.52, \$8.52, and \$9.30 respectively), (4) providing participants choices of incentives to broaden acceptability of incentives (PayTM – e-cash widely used in India, and connected to mobile number, or Amazon.co.in gift-code) (5) utilizing a drawing prize system of one in twenty \$15.50 incentives to reinforce online study assessment completion and minimize attrition (at 3,6,12,18 months) and being entered into a drawing at months 9 and 15 (for one of twenty \$15.50 incentives) for verifying or updating contact information.

This protocol aims to recruit a diverse sample of men who do not know their current HIV status (i.e., report that they have either never been tested for HIV, are unaware of HIV test results, or are HIV-negative with last HIV test greater than or equal to six months ago, and have engaged in anal sex since last HIV test). Therefore, inclusion criteria will be

(1) ≥18 years old; (2) live or work in the Mumbai metropolitan area, including Thane; (3) fluent in Hindi or English, (4) identify as cis male, (5) anal sex with men in past 1 year; (6) (a) report that they have either never tested for HIV, (b) are unaware of HIV test results, or (c) are HIV-negative with last HIV test >6 months ago and anal sex since last test; (7) able to provide and verify a WhatsApp mobile number and email address; (8) willing to answer online surveys for 18 months; and (9) have not participated in a prior HIV research study (by self-report).

We will exclude individuals who (1) are unwilling to consent/ assent to the study, (2) do not verify their WhatsApp account, and (3) have used services at HST within the past year.

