A1d. Special vulnerable populations. We will not include fetuses, neonates, children, pregnant women, prisoners, or institutionalized individuals in the proposed research. Men who have sex with men are vulnerable due to their status as a stigmatized population in society and further stigmatization could be possible if their status as a participant in an HIV prevention intervention is revealed. In the following sections, we discuss these risks and procedures to minimize them and believe that the risks to participation in the proposed study are minimal.

A1e. Study group assignment procedures, and rationale for intervention's dose, frequency and administration. Subjects meeting all eligibility criteria will be randomized to one of three study arms. Participants will be assigned either to CHALO! 2.0 (intervention), to an Attention-Matched Control, or to a Digital Coupon for free HIV testing only arm. Randomization will occur in a random blocked design, stratified by HIV testing history (never tested/unaware of results vs. previously tested). To minimize bias in treatment group allocation, the data manager will store the allocation sequence using a password-protected file, and has no contact with study participants. Participants will receive automated messages with online

survey links to complete study assessments, and study staff extracting medical record/log data to ascertain linkage-to-care outcomes, will be blinded to treatment group allocation and will have no contact with study participants.

During the 12-weeks intervention period, participants assigned to either CHALO! 2.0 (intervention) or the Attention-Matched Control (AM) arm will be exposed to twice-weekly digital messaging, including text, brief videos, inform graphics, etc. via an online messaging site. However, the digital message for participants in the CHALO! 2.0 arm will include information regarding HIV testing, accessing treatment and prevention care with a focus on targeting information, motivation, and behavioral skills, while the information in the AM arm will focus on general health topics (e.g., diabetes, obesity, nutrition, exercise). Participants in the digital coupon only arm will not receive any messages aside from the reminders to complete study assessments. We are providing twice weekly contents as this was determined in the past to be acceptable, not intrusive and higher frequency may actually be detrimental.

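### Sections 7 and A1e define the randomisation strata differently, and Section 7 leaves some eligible men who do not know their test result without a stratum

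*Combined protocol and SAP*

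**What the plan says.** Prior HIV testing history is the only stratification factor. It is defined twice:

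- Section 7 (Randomization and blinding) uses a fixed block size "to stratify randomization by prior HIV testing history (never tested vs. not tested in >6 months").
- A1e (Study group assignment procedures) describes a blocked design "stratified by HIV testing history (never tested/unaware of results vs. previously tested").

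Section 7 and A1e both state: "Subjects meeting all eligibility criteria will be randomized to one of three study arms". Every eligible man therefore needs a stratum.

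Criterion 6 in the Methods (Participants) admits three groups. Group (a) has never been tested. The other two are given as "b) are unaware of HIV test results, or (c) are HIV-negative with last HIV test ≥ 6 months ago at any time", with anal sex since the last test. No time limit is attached to group (b).

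A1c repeats the three groups but gives the cut-off for known negatives in two ways. Its prose has "are HIV-negative with last HIV test greater than or equal to six months ago"; its numbered list has "c) are HIV-negative with last HIV test >6 months ago and anal sex since last test". A1b, describing the population, also uses more than 6 months.

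**The concern.** A stratified allocation list works only if each eligible participant belongs to exactly one stratum and everyone who reads the protocol would choose the same one. Here two sections give different rules, neither is said to govern, and the Section 7 rule does not cover the whole eligible population. The group caught by this is 6(b), the men who tested but do not know the result.

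What is at stake is reproducibility and traceability. The data manager who assigns participants has no single rule to follow for 6(b), the allocation cannot be reconstructed from the protocol, and a table or model by stratum could not be defined without asking which rule was used. The factor is a natural one to carry into the analysis, because the Aim 1 primary outcome is itself a verified HIV test within 6 months. Yet the planned models do not name it.

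**Working it through.** No sample size, power or alpha figure depends on this point, so there is no figure of the plan to reproduce. The check is to take each possible testing history, assume all other criteria are met (including anal sex since the last test), and read off eligibility and stratum from each passage. Three, six and nine months stand for below, at and above the cut-off.

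| Testing history | Eligible: Methods 6 and A1c prose (≥6) | Eligible: A1c list (>6) | Section 7 stratum | A1e stratum |
|---|---|---|---|---|
| Never tested | yes | yes | first | first |
| Known negative, 3 months ago | no | no | not needed | not needed |
| Known negative, exactly 6 months ago | yes | no | none | second |
| Known negative, 9 months ago | yes | yes | second | second |
| Result unknown, 3 months ago | yes | yes | none | first* |
| Result unknown, exactly 6 months ago | yes | yes | none | first* |
| Result unknown, 9 months ago | yes | yes | second | first* |

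*If being unaware of the result takes precedence. Read literally, such a man also counts as previously tested, so A1e covers everyone but its two categories overlap.

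Four results follow.

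1. **Conflict.** A man unaware of a result from more than 6 months ago is in opposite strata under the two sections.
2. **Gap.** A man unaware of a result from 6 months ago or less is eligible under every version of criterion 6, yet fits neither Section 7 category.
3. **Boundary.** A known negative at exactly 6 months is eligible under the Methods and the A1c prose and ineligible under the A1c list. He has no stratum in Section 7.
4. **Agreement elsewhere.** Never-tested men, and known negatives beyond 6 months, are placed alike by both sections.

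Use of the stratum in the analysis: Section 13.1 specifies two-sample chi-square tests, then logistic and Poisson regression adjusted for Table 2 covariates. Section 13.3 follows the same pattern for Aim 2, with chi-square tests and logistic regression. The covariate rows of Table 2 include no prior-testing item; HIV testing appears there as an outcome, with collection at month 0. Section 8.1 lists prior testing among the survey data and could be read as counting it a covariate, but no section names the stratification factor as a model term.

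**The case against.** The strongest reply is that Section 7 is shorthand for A1e. A1e, with unaware taking precedence, places every eligible man, so a workable rule already exists and nobody is unplaceable if that is what was programmed. This largely stands, and it is why the repair is to bring Section 7 into line with A1e. It does not remove the point. Read as written, the Section 7 wording sends unaware men with an older test to the other stratum, and A1e needs the precedence stated.

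A second reply is that no planned analysis is by stratum, so an ambiguous label does no harm to the results. That stands for the chi-square tests. It also shows a related omission, since a factor used to restrict randomisation would ordinarily be carried into the regression models.

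A reader might infer that the promised balance between arms is lost for men unaware of their result. The documents do not support this. Neither definition makes group (b) a stratum of its own, so no separate balance was promised for it, and whichever single rule is applied, blocking balances the arms within that rule's strata.

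The boundary issue is fairly called marginal: it concerns one point on a self-reported date.

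**Conclusion.** The point holds as a conflict and a gap in the operating rule for the only stratification factor, with a minor inconsistency in the 6-month cut-off. It is worth correcting, but it does not threaten the trial's validity.

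A reader might infer bias in the comparison of arms, or a loss of power. Neither follows. Assignment is random within whichever strata are used, and the power statements in 13.2 and 13.4 rest on two-sample comparisons at a two-tailed alpha of .025 that do not involve the stratum.

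The number of men concerned cannot be computed, because the documents give no share for group (b). If one assumed 2% to 10% of the 1,000 participants, group (b) would be 1,000 × 0.02 = 20 to 1,000 × 0.10 = 100 men. That is an assumed size for the group, not a count of men wrongly placed. Only those with a test 6 months old or less lack a stratum, and only under Section 7; the others have a stratum under each rule and are ambiguous only until one rule is chosen. If A1e was the rule implemented, with unaware taking precedence, none is unplaceable. The conclusion rests on the wording alone and on the absence of any statement about which section governs.

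**What to change.** 1. Use one definition in Section 7 and A1e, tied to criterion 6. Stratum 1 is 6(a) never tested or 6(b) unaware of results, whatever the test date. Stratum 2 is 6(c) known negative. State that 6(b) takes precedence, so that the strata do not overlap. This keeps A1e's grouping and removes the time cut-off from the stratum definition.
2. Choose one wording of the 6-month cut-off and use it in the Methods (Participants), A1b, both places in A1c, and Section 7 if a cut-off remains there.
3. Store the stratum used at randomisation as a field in the study database.
4. Add that recorded stratum as a factor in the Aim 1 and Aim 2 regression models. The chi-square comparisons can stay as planned.
5. If enrolment has begun, document which definition was applied and keep the recorded strata; re-deriving them from screener answers would bring in a second definition. Section 6.7 remarks that participants may already be passing on enrolment links, so this should be settled first.

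The cost is a few wording edits, one stored field and one extra model term. Nobody needs to be re-randomised, and the sample size is unaffected.
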